4.4 Exploratory efficacy endpoints

- Neuroimaging: Progression of retinal nerve fiber thinning as detected by optical coherence tomography (OCT).
- Cognitive dysfunction as assessed by Symbol Digit Modality Test (SDMT).
- Neurological disability as assessed by MS functional composite (MSFC) scale.
- Biological/immunological endpoints:
 - Changes in cerebrospinal fluid (CSF) albumin quotient (ROS are known to disrupt endothelial tight junctions; which may be measured as increase in CSF albumin quotient)
 - Changes in CSF biomarkers of activated/pro-inflammatory microglia/monocytes (sCD14)
 - Changes in CSF lactate/pyruvate ratio, as a biomarker of extra-mitochondrial glucose metabolism

- Changes in CSF growth differentiation factor 15 (GDF15), as a putative biomarker of mitochondrial dysfunction
- Changes in CSF neurofilament light chain (NF-L), a biomarker of axonal damage.

5 Design and type of the study

This is a Phase I/II safety and efficacy trial with an adaptive trial design: one year of pre-treatment baseline period serves the dual purpose of collecting patient-specific biomarkers of disease progression and collecting longitudinal neuroimaging and clinical data for selection of primary outcome measures. This baseline period is then followed by a double-blind, idebenone versus placebo treatment phase for a total of 2 years.

6 Sample size considerations

6.1 Original sample size calculation

Assumptions for the initial sample size calculation were:

1. Rate of development of CNS atrophy in early PP-MS patients is equivalent, or greater than the rate of development of brain atrophy in relapsing remitting MS (RR-MS) patients and similar to rate of development of brain atrophy in secondary progressive MS (SP-MS) patients (Fox, Jenkins et al. 2000).
2. Rate of development of brain atrophy in PP-MS patients varies considerably between individuals, ranging from +1.8%/year to -3.6%/year (Mean -1.03%, SD 1.3%) for brain parenchymal fraction (BPF) and from +1.7%/year to -4.2%/year (Mean -1.50%, SD 1.6%) for grey matter fraction (Sastre-Garriga, Ingle et al. 2005).
3. Within 5 years of follow-up, the rate of development of brain atrophy, ventricular atrophy, cervical cord atrophy and the rate of accumulation of T2LV and T1LV seem to be significantly more stable intra-individually than inter-individually (Ingle, Stevenson et al. 2003), although the intra-individual coefficient of variation values are not provided in this publication.
4. Due to these inter-individual differences in the rate of accumulation of brain atrophy, the reported sample size estimates in SP-MS patients utilizing changes in brain atrophy detected by SIENA methodology applied to 1.5T MRI scans, indicates that to detect 50% therapeutic effect in a therapeutic trial of 2 year duration with 80% power and 5% significance, the minimum number of subjects is 33 per arm (Altmann, Jasperse et al. 2008). The relevant data from this recent publication using SIENA methodology for calculation of whole brain atrophy in SP-MS patients by Altmann, Jasperse et al. are summarized in the table below (selected conditions for current trial are highlighted)

Duration of therapy	Expected therapeutic effect:	90% power			80% power		
		30%	40%	50%	30%	40%	50%

		effect	effect	effect	effect	effect	Effect
1 year	Min# subj/arm	212	120	77	158	89	57
2 years	Min# subj/arm	123	69	45	92	52	33
3 years	Min# subj/arm	107	60	39	80	45	29

Collecting at least 12 months of pre-treatment baseline volumetric MRI data (i.e. rate of development of brain atrophy, gray matter atrophy, ventricular enlargement and spinal cord atrophy) and clinical data will allow us to calculate individualized rates of CNS tissue destruction and disability progression. Based on the data described under 1-3, employing such individualized rates of development of CNS tissue destruction for the determination of therapeutic effect between active drug and placebo is expected to significantly increase the power for detection of group differences, effectively decreasing the number of subjects necessary for demonstrating therapeutic efficacy of an experimental neuroprotective therapy. Additionally, employing more sensitive methodology (3T magnet strength) and novel analyses (e.g. volumetric analysis of entire cervical spinal cord) may further increase power for detection of group differences.

However, longitudinal data on a PP-MS cohort that could be utilized for exact sample size analysis was not available and the only longitudinal data that were published at the inception of this trial and could be utilized for sample size calculation were those based on whole brain atrophy as detected by SIENA methodology. Therefore, we used published sample size estimates for the SP-MS patients (Altmann, Jasperse et al. 2008) and targeted patient accrual to reach 66 treated patients (33 per arm).

6.2 New sample size calculation

In 2016, a pre-determined analysis of the 58 outcome measures collected in 1 year pre-treatment baseline period on first ≥ 30 IPPOMS patients was performed and published and validated these findings with the 2 validation cohorts consisting of 34 remaining IPPOMS patients and 29 SP-MS patients from RIVITALISE trial (Kosa, Ghazali et al. 2016). This analysis demonstrated that above-stated assumptions or the original sample size calculation were incorrect, that brain atrophy measured by SIENA technology was not more sensitive than clinical outcomes. Instead, based on this pre-defined analysis we selected CombiWISE as primary outcome and brain ventricular atrophy measured by LesionTOADS methodology as secondary outcome.

Up to 85 subjects are planned to be recruited based on current sample size calculation, to account for 20% drop-out and final number of treated subjects 33 per arm (66 total). These recruitment numbers were already achieved and interim analysis of the blinded data of the outcomes showed enhanced, rather than diminished power of new primary outcome (CombiWISE) in comparison to original default primary outcome (Brain atrophy measured by SIENA).

The new power analysis for CombiWISE, EDSS and ventricular volume change has been published for both within-group and between-group designs (Kosa, Ghazali et al. 2016). Using absolute change in the CombiWISE AUC outcome determined from the pre-treatment baseline data in IPPOMS cohort, following power calculation for AUC was derived:

Drug effect	CombiWISE AUC (untreated)	CombiWISE AUC (treated)	CombiWISE AUC (difference)	Actual Power	N Pairs	Distribution	Normal
50%	51.24	25.62	25.62	80.7	28	Method	Exact
45%	51.24	28.18	23.06	80.6	34	Number of Sides	2
40%	51.24	30.75	20.50	80.2	42	Standard Deviation	46.2
35%	51.24	33.31	17.94	80.7	55	Correlation	0.5
30%	51.24	35.87	15.37	80.1	73	Nominal Power	0.8
25%	51.24	38.43	12.81	80.4	105	Null Difference	0
20%	51.24	40.99	10.25	80.2	162	Alpha	0.05

This demonstrates that substituting default primary outcome (Brain atrophy measured by SIENA (Altmann, Jasperse et al. 2008)) with CombiWISE primary outcome will significantly enhance power of the IPPOMS trial from estimated 80% of power to detect at least 50% drug effect to more than 80% power to detect at least 40% drug effect. Additionally, while brain atrophy measured by SIENA does not correlate with clinical outcomes, CombiWISE has strong, highly significant correlations with EDSS, which is used for regulatory approval of MS treatments, both in cross-sectional and longitudinal paradigms (i.e. yearly change in CombiWISE correlated with yearly change in EDSS). Therefore, CombiWISE can predict efficacy on EDSS outcome, but does so in considerably smaller cohorts and/or trials of shorter duration (Kosa, Ghazali et al. 2016).

7 Statistical hypotheses

The primary goal of this study is to determine the safety of long-term (24 months) idebenone therapy at 2250 mg/day in patients with PP-MS.

The primary efficacy objective of this final analysis of the IPPoMS study is to investigate the effect of idebenone compared with placebo on the disability progression using the CombiWISE score with the following statistical hypotheses:

H_0 : There is no difference between idebenone and placebo in the disability progression during the 2-year treatment period.

H_A : The disability progression in idebenone-treated patients is slower than in the placebo-treated patients during the 2-year treatment period.

In addition to the difference between the treatment groups, the within-group changes in each treatment group will be evaluated by comparing the disability progression during the pre-treatment period to the progression during the treatment period.

8 Analysis sets

The data will be analyzed using at least the following datasets:

- *Intention-To-Treat (ITT) Population*

The Intent-To-Treat (ITT) population includes all randomized patients who have at least one post-baseline (post Month 0) efficacy assessment. The patients will be grouped by the randomized treatment group. The ITT population will be used for the analysis of the efficacy endpoints.

- *Completer Population*

The Completer population includes all randomized patients who completed the study and have valid efficacy assessments up to Month 24. The patients will be grouped by the randomized treatment group. The Completer population will be used for the secondary analysis of the efficacy endpoints.

- *Pre-Treatment Phase Safety Population*

The Pre-Treatment Phase Safety population includes all patients who were enrolled to the study. The patients will be grouped by the treatment actually received in the Double-Blind Phase. The Pre-Treatment Safety population will be used for the safety analysis of the pre-treatment baseline phase.

- *Safety Population*

The Safety population includes all patients who got at least one dose of idebenone or placebo during the double-blind phase. The patients will be grouped by the treatment actually received. The Safety population will be used for the analysis of the safety data from the double-blind phase.

9 General statistical considerations

In general, all data collected in the study database will be summarized by descriptive statistics. Continuous data will be summarized using the mean, standard deviation, standard error of the mean, median, minimum and maximum. Categorical data will be presented in contingency tables with frequencies and percentages.

All hypotheses tests and confidence intervals in this report are two-sided and statistical significance will be declared for p-values below 5%, unless specified otherwise. This study has one pre-defined endpoint. Due to the exploratory nature of the study, no adjustment of the statistical significance level due to multiple secondary endpoints will be done.

10 Demographic and other Baseline characteristics

Demographic and Baseline characteristics will be presented with descriptive statistics for the ITT and Safety populations. These characteristics will be based on the assessment at the study entry (Month -12).

The following endpoints will be summarized:

- Baseline age
- Age at disease onset

-
- Time since disease onset at baseline
 - Body Mass Index
 - History of mononucleosis
 - European ancestry
 - Family history of MS
 - Smoking history

11 Concomitant medication/treatment

All concomitant medications will be listed.

12 Extent of exposure to study medication

The extent of exposure to the study medication will be summarized by tabulating the following:

- The number of patients exposed to study treatment (idebenone or placebo) during the double-blind phase.
- Duration of exposure (days): exposure to study treatment (idebenone or placebo), where the duration is calculated as date of last dose minus date of first dose during the double-blind phase. In addition, the duration of follow-up during the pre-treatment baseline phase will be calculated as date of first dose during the double-blind phase minus date of first visit (Month -12). The durations will be summarized with descriptive statistics separately for pre-treatment baseline phase and for the double-blind phase.
- Total exposure to study treatment, expressed as person years (sum of duration of exposure to study treatment over all patients in days divided by 365.25, classified by treatment group). The total exposure will be calculated for the double-blind phase and summarized by treatment group. For the pre-treatment baseline phase, the total follow-up time will be calculated similarly, and summarized by treatment group and overall.

13 Analysis of efficacy

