Figure 3: There are two possible ways how changes in outcomes collected every 6 months (e.g., primary outcome: CombiWISE) can be analyzed: 1. As a change in regression slopes (left panel) or 2. As a change in AUC (right panel). There are two major problems with regression slopes: First, the baseline pre-treatment period slope is derived only from 3 measurements. Because these measurements are spread equally apart, the least squares linear regression slopes are calculated only from 1st and 3rd measurement, whereas the middle (2nd) measurement affects only the intercept. Consequently, even though we have three baseline measurements, only two of them would be de-facto utilized for final outcome comparison. Furthermore, as depicted in the left panel, if the drug has both neuroprotective effect (which decreases slope) and promotes structural or functional repair (which decreases intercept), comparing slopes would de-facto ignore the latter potentially important mechanism of action (MOA). In contrast, measuring changes in disability progression between untreated and treated period using AUC (right panel) eliminates both stated disadvantages of progression slopes. This method uses all measured data and correctly deals with the improvements in disability by subtracting parts of the curve that are below the baseline (i.e. CombiWISE measure at the initiation of therapy) from the AUC part that is above the baseline.

The only problem with AUC is unequal length of the compared periods: while pre-treatment baseline period has 1-year length, the treatment period for IPPOMS trial has length of 2 years. It may be intuitive to divide 2-year AUC period by 2 to obtain equivalent yearly measurements, but that is incorrect. As depicted in the left panel, if the progression slopes were linear, the AUC derived from 2-year period needs to be divided by 4 to get equivalent yearly AUC progression. We have validated correctness of this adjustment by analyzing blinded 2 year CombiWISE data from 50 patients who finished 2 years of study and by comparing average AUC derived from splitting Year 1 and Year 2 of this longitudinal cohort, versus calculating AUC from the entire 2-year period. We observed that these two measurements strongly correlate with each other ($r^2=0.905$) with following linear regression formula:

$$Y = -0.77 + 3.96 * X, \text{ where } X \text{ is average yearly AUC and } Y \text{ is 2-year AUC measured in the same patient.}$$

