The AUC values will be calculated for both the pre-treatment baseline phase (from Months -12, -6 and 0) and for the double-blind phase (from Months 0, 6, 12, 18 and 24). For each of the AUC values, at least two valid CombiWISE scores during the phase in question are required. If less than two values AUC values are available for any of the two phases, the AUC score will be set as missing. In addition, if the first value of the phase in question is missing, the CombiWISE score will be set as missing.

Linear trapezoidal method will be used to calculate the AUC values. For each time interval (time between two visits), the AUC is calculated as $0.5 \times (Y_1 + Y_2) \times (t_2 - t_1)$, where Y_1 and Y_2 are the CombiWISE scores (as changes from baseline) at the beginning and end of the interval and t_1 and t_2 are the start and stop dates of the interval. The time will be converted to years (number of days divided by 365.25) for the AUC calculation. The baseline for the pre-treatment period is the visit scheduled at the beginning of the pre-treatment period (Month -12) and the baseline for the double-blind period is the visit at Month 0.

In case of intermittent missing data between two non-missing visits, the formula for linear trapezoidal method will be used as such. In case of premature discontinuations, the AUC values after the time of discontinuation will be set as missing.

After these calculations, the AUC values calculated for the different periods will be summed over the pre-treatment baseline phase (Month -12 to Month 0) and over the double-blind phase (Month 0 to Month 24). Because the follow-up times can vary from patient to patient, the AUC values will be made comparable by scaling them using the follow-up time. The scaling will be done by dividing the AUC value by the square of the actual duration of each of the phases. For the pre-treatment baseline phase, the AUC will be scaled as $AUC/[t_0 - t_{-12}]^2$, where t_0 and t_{-12} are the dates of visits at Month 0 and Month -12, respectively. For the double-blind phase, the AUC will be scaled as $AUC/[t_{last} - t_0]^2$, where t_{last} and t_0 are the dates of the last visit and the visit at Month 0, respectively. Similarly as above, the time will be converted to years. The scaled AUCs will be used in all statistical analyses.

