13.1 Primary endpoint: AUCs of CombiWISE scores

13.1.1 Primary analysis

The AUCs of the CombiWISE scores will be analyzed using an Analysis of Covariance (ANCOVA) model with the AUC of the pre-treatment CombiWISE scores, Baseline (Month 0) CombiWISE score and Baseline (Month 0) age as covariates.

The incomplete data in the CombiWISE scores during the 2-year treatment period will be managed with the single imputation algorithm defined in Section 4.2.

In addition to the primary analysis comparing the between-group difference, the within group changes will be tested using paired t-test within each treatment group. The t-tests will be based on Satterthwaite's approximation.

The analyses will be conducted both using the ITT population (primary) and Completer population (secondary).

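### The power table cited for a 40% effect is a paired calculation needing 42 pairs; the trial plans 33 per arm, and no between-arm power is shown for the primary ANCOVA

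*SAP*

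**What the plan says.** SAP 6.2 and Protocol 11.7 print the same new power table for CombiWISE. Its inputs are described as "Using absolute change in the CombiWISE AUC outcome determined from the pre-treatment baseline data in IPPOMS cohort". The table gives an untreated mean of 51.24, an SD of 46.2, a correlation of 0.5, two sides, alpha 0.05 and a column of sample sizes headed N Pairs. The 40% row shows 42 pairs and 80.2% power. Both documents then say the table demonstrates that replacing SIENA brain atrophy with CombiWISE takes the trial from 80% power for a 50% effect "to more than 80% power to detect at least 40% drug effect".

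SAP 6.2 gives the planned size as "final number of treated subjects 33 per arm (66 total"), and Protocol 11.6 gives the same number. Both documents add that the new power analysis for CombiWISE, EDSS and ventricular volume "has been published for both within-group and between-group designs", but neither reports an input or a result from the between-group version.

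The primary analysis in SAP 13.1.1 compares the arms: "The AUCs of the CombiWISE scores will be analyzed using an Analysis of Covariance (ANCOVA) model". Its outcome is the scaled AUC of SAP 4.2: "The scaling will be done by dividing the AUC value by the square of the actual duration of each of the phases". The paired test is additional: "the within group changes will be tested using paired t-test within each treatment group". Protocol 11.7 itself said that a power analysis for a newly chosen primary outcome would use a two-sample t-test.

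**The concern.** The table and the sentence drawn from it do not match on three counts.

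- **Design.** A calculation in pairs with a within-pair correlation fits the additional within-arm test. It does not fit the primary between-arm comparison.
- **Number.** The 40% row needs 42 pairs and the 45% row needs 34. An idebenone arm of 33 supplies neither.
- **Unit.** The claimed improvement from 50% to 40% sets a SIENA figure in patients per arm (33, from the table in SAP 6.1) against a count of pairs.

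The sentence tells the reader that a true 40% effect would be missed less than one time in five. It is the only power figure in either document for the primary CombiWISE comparison. Protocol 7.6 records that no significant efficacy was found, so a reader judging what the trial could have missed will rely on it. The choice of CombiWISE as primary outcome rests on other analyses and is not in question.

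**Working it through.** **Step 1: reproduce the table.** For a paired t-test, the SD of the difference is 46.2 × √(2 × (1 − 0.5)) = 46.2. The noncentrality is (difference / 46.2) × √n on n − 1 degrees of freedom, two-sided 5%. For the 40% row this is (20.50 / 46.2) × √42 = 2.876 on 41 df.

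| Effect | Difference | N pairs | Stated power | Recomputed |
|---|---|---|---|---|
| 50% | 25.62 | 28 | 0.807 | 0.807 |
| 45% | 23.06 | 34 | 0.806 | 0.806 |
| 40% | 20.50 | 42 | 0.802 | 0.802 |
| 35% | 17.94 | 55 | 0.807 | 0.807 |
| 30% | 15.37 | 73 | 0.801 | 0.801 |
| 25% | 12.81 | 105 | 0.804 | 0.804 |
| 20% | 10.25 | 162 | 0.802 | 0.802 |

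Every row matches, and one pair fewer drops each row below 80%. Read instead as patients per arm in a two-sample t-test, the rows give 51% to 53% power (52.0% for 42 per arm). The table is therefore a paired calculation.

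**Step 2: same method, 33 pairs.** Taking the difference as the stated percentage of 51.24:

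- 40%: 0.40 × 51.24 = 20.50; noncentrality (20.50 / 46.2) × √33 = 2.55 on 32 df; power 69.5%.
- 45%: power 79.4%.
- 50%: power 87.0%.
- 80% power is reached at a difference of 23.236, and 23.236 / 51.24 = 45.3%.

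Counting all 66 patients as pairs would give 94.4% at 40%, but pairs from placebo patients contain no drug effect. If a pair meant one idebenone and one placebo patient, there would still be only 33.

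**Step 3: what the primary test needs.** For 33 per arm the noncentrality is difference / (s × √(2/33)), where s is the ANCOVA residual SD. Power of 80% for a difference of 20.50 on 64 df requires s ≤ 29.27 (29.25 on 61 df, allowing for group and three covariates). As a fraction of the untreated mean, 29.27 / 51.24 = 0.571. Against the table's SD, 29.27 / 46.2 = 63%.

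**Step 4: illustration only.** Neither document gives the SD of the scaled 2-year AUC or its correlation R with the covariates. If the 1-year SD of 46.2 carried over unchanged, the residual SD would be 46.2 × √(1 − R²):

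| Assumed R | Residual SD | Power at 40% |
|---|---|---|
| 0 | 46.2 | 43% |
| 0.5 | 40.0 | 54% |
| 0.7 | 33.0 | 70% |
| 0.78 | 28.9 | 81% |

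The 80% line is crossed at R of about 0.77. A smaller SD for the scaled 2-year AUC would raise every figure, so this is not a range for the trial's power.

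**The case against.** The strongest reply is that the sentence may be roughly right for the primary ANCOVA, because the scaled 2-year AUC should be less noisy than the 1-year AUC. With independent visit error of variance σ², the trapezoidal weights on change from baseline give an error variance of 0.875σ² for the 1-year AUC. For the 2-year AUC divided by 4 they give 3.875σ² / 16 = 0.242σ². The error SD falls to √(0.242 / 0.875) = 53%, while a linear slope contributes equally to both. Simulated linear patient slopes plus visit error, calibrated to a 1-year SD of 46.2, gave power at 40% of about 74% or more, often above 80%; a random-walk course gave about 69%. This stands as a reason to treat the 43% and 54% figures as pessimistic. These models are assumptions too, and they do not make the table a demonstration of the claim.

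Other points have partial force. A between-group analysis is cited as published, and SAP 6.2 refers to a blinded interim analysis showing enhanced power; but neither document prints a figure from either. The 33 per arm is a planned number, and Protocol 11.5 describes 35 + 34 = 69 patients with pre-treatment data; but 35 pairs still give only 72%. The table's arithmetic is correct, so the fault lies in the inference drawn from it. Recruitment was complete and the analysis has since been reported, so correcting the sentence changes no sample size, test or decision.

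**Conclusion.** The concern holds. The table does not demonstrate more than 80% power for a 40% effect on either reading. On its own paired terms, 33 pairs give 69.5%, and 80% needs a 45.3% effect; this uses only the documents' inputs and the planned arm size. For the primary between-arm ANCOVA the power at 40% is not shown. It could be below or above 80%, depending on the SD of the scaled 2-year AUC and its correlation with the covariates, which the documents do not give. What can be said without those inputs is the condition: at 33 per arm and two-sided 5%, the residual SD must be at most about 0.57 of the untreated mean. This is a correction to a stated figure and does not criticise the endpoint or the test.

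**What to change.** In SAP 6.2 and Protocol 11.7:

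1. Label the table as a within-patient calculation (pre-treatment versus on-treatment) and state the unit of the AUC.
2. Withdraw the statement that it demonstrates more than 80% power at a 40% effect.
3. Replace it with a two-sample or ANCOVA calculation at 33 per arm, using the blinded pooled SD of the scaled 2-year AUC and its correlation with the pre-treatment AUC. Protocol 11.2 shows that suitable data were in hand, since it describes "analyzing blinded 2 year CombiWISE data from 50 patients who finished 2 years of study". Alternatively, quote the inputs and result of the published between-group analysis.
4. If neither is done, give only the residual-SD condition (at most about 0.57 of the untreated mean), with no fixed power range.

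The cost is text in two places and one blinded SD and correlation. No extra patients are needed and the test does not change. The stated power may become less favourable.
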